## **2. Risk/Benefit Assessment**

### **2.1. Research Procedures Involving Study Subjects**

**Recruitment:** Latino Task Force/Unidos en Salud Community Health Workers (CHWs) in partnership with bilingual bicultural UCSF study staff will recruit eligible participants among people who are receiving services or attending community cultural or health fairs at Latino Task Force (LTF) sites or CBOs affiliated with the Latino Task Force.

**CHW Counseling:** Participants in Aim 2 and Aim 3 will have a 20-minute counseling session with a community health worker. The content of the session will consist of the 5A's technique and will be informed by adaptations made in Aim 1.

**Text-message nudge:** Participants will receive a text message about RSV vaccination with a scheduling and informational link. The text-message will be sent on behalf of the Latino Task Force.

**Questionnaires:** At baseline and endline participants will complete a survey on demographics, vaccine confidence, hesitancy, and social networks. Names will not be collected in the social-network survey.

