#### **4.4.2. Study Population**

CHWs and study staff will recruit from people accessing services or community fairs at LTF-affiliated CBOs or attending cultural events in San Francisco. Study inclusion criteria include Latino adults 18-49. Detailed inclusion criteria are outlined in section **5.1.1**.

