#### **4.4.3. Study Design Aim 3 and Intervention Groups**

This is a two-arm type 1 effectiveness-implementation RCT randomized at the level of the individual (Figure 5) with the following **study groups**:

**Arm 1: Text message from a CBO:** Participants will receive an educational flyer from a CHW about RSV vaccination and how people in their network can schedule vaccines and the 'LTF hotline' for help with navigation if needed. Then 4 weeks later receive a text-message nudge, with message content based on findings in Aim 1b. As in Aim 2, the text message will also provide a flyer with vaccine information, eligibility, and scheduling from the LTF.

**Arm 2: CHW 'activation' counseling with text-message nudge:** At enrollment participants will receive the same flyer as in Group 1. Then, within 2 weeks of enrollment participants will have a 20-minute scripted conversation (in person or phone) grounded in motivational interviewing principals of Five A's. CHWs will assess participants beliefs and knowledge about RSV and vaccine effectiveness, safety, eligibility, *and* interest and barriers in recommending RSV vaccination to their friends or family. Then they will advise how to initiate conversations about RSV vaccination. CHWs will then assist, by assessing personal barriers to discussing vaccination with older adults. Then arrange next steps: CHWs will write down an action plan and give it to the participant. CHWs will also provide a hotline number for participants or their contacts to use for questions or support scheduling an appointment. Participants will receive a text-message nudge with scheduling and information 1 month after enrollment.

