**Table 4: Inclusion and Exclusion Criteria**

Study	Inclusion Criteria	Exclusion Criteria
Aim 1		
RSV Vaccine Confidence Survey	(a) Adult age $\geq 18$ years (b) Speaks Spanish or English	Not able to provide informed consent
Community Advisory Groups for Adaptation of Intervention	1. Group 1: a. age $\geq 60$ years b. speaks Spanish or English c. self-identifies as Latino/a/e/x and/or indigenous group from Latin America d. lives or works in San Francisco County or Daly City and able to come to in-person meetings in San Francisco 2. Group 2: a. age 18-50 b. speaks Spanish or English c. Self-identifies as Latino/a/e/x and/or indigenous group from Latin America d. lives or works in San Francisco or Daly City and able to come to in-person meetings in San Francisco	Not able to provide informed consent  Planning on moving out of San Francisco or Daly City area in 12 months
In Depth Interviews (Aim 1)	(a) Self-identifies as Latino/a/e/x and/or indigenous group from Latin America (b) Speaks Spanish or English (c) Age $\geq 18$ years	Not able to provide informed consent
Aim 2 'Motivate Trial'	Inclusion Criteria: (a) Age $\geq 50$ years (b) Self-identify as Latino/a/x and/or indigenous groups from Latin America	(a) Intent to move outside of San Francisco in the next year

	
 
(c) Eligible for RSV vaccination per current CDC/ACIP recommendations*
 
(c) Fluent in Spanish or English
 
(d) Has not received the RSV vaccine
 
(e) Has a cell phone
 
(f) Lives or works in San Francisco or Daly City
 
(f) Able to provide informed consent
 
 
* CDC/ACIP Eligibility for RSV Vaccination:
 
 
(1) Age 75 years and older
 
(2) Age 50-74 and one of the following medical comorbidities: cardiovascular disease (e.g. coronary artery disease), lung disease (e.g. COPD, asthma), advanced chronic kidney disease, diabetes, liver disorders, neurologic or neuromuscular conditions, hematologic disorders, moderate or severe immune compromise
 
	
 
(b) Nursing home resident
 
(c) Household member participating in Aim 1 or 2
 
(d) Unable to provide consent
 

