Aim 3 'Activate Trial'	
Inclusion Criteria:
 
 
(a) Age 18-49 years
 
(b) Self-identify as Latino/a/x and/or indigenous groups from Latin America
 
(c) Fluent in English or Spanish
 
(e) Has a cell phone
 
(f) Has <math>\geq 1</math> family member or friend 50 years or older who they have seen or spoken to for <math>\geq 15</math> minutes in the last 6 months and who lives in the United States
 
	
Exclusion Criteria:
 
 
(a) Household member enrolled in Aim 1 or 2
 
(b) Unable to provide consent
 

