## 7.2.2. Randomization and Interventions for 'Activate' Trial (Aim 3)

In a parallel structure to Aim 2 we will conduct a randomized trial of the intervention components (CHW counseling and text-message from a CBO) adapted from the Development phase (aim 1). This is a two-arm type 1 effectiveness-implementation RCT randomized at the level of the individual with the following study groups outlined in section 4.4.3:

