#### **9.3.1. Aim 3 Sample size considerations**

As with the secondary outcomes for Aim 2, statistical power will depend of participation in the 60-day follow-up interview. Assuming 10% attrition for the 175 participants in each arm, we will be able to detect a minimum ITT effect of 11% for any binary outcomes. For our primary outcome, assuming a standard deviation (Standard Deviation) of 0.3 for the proportion of adults contacted, with 175 participants/arm we will have 80% power (using  $\alpha=0.05$ ) to detect at least a 10% absolute increase (e.g. from 30% to 40%) in the average proportion of older adult contacts with whom RSV vaccination was discussed.

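### The Activate trial's household exclusion omits Activate itself, so two housemates can be randomized to opposite arms

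*Protocol*

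**What the plan says.** Table 4 (Protocol 5.1.1) sets eligibility row by row. The Motivate row excludes anyone with a "Household member participating in Aim 1 or 2". Because Motivate is Aim 2, this bars a second person from a household already in Motivate. The Activate row excludes anyone with a "Household member enrolled in Aim 1 or 2". Activate is Aim 3, which that wording leaves out.

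Section 7.2.2 describes Activate as an "RCT randomized at the level of the individual with the following study groups outlined in section 4.4.3". Section 6.1 specifies computer-generated blocks of 2 stratified by sex, with no household factor. Section 4.4.2 recruits people using services or at "community fairs at LTF-affiliated CBOs or attending cultural events in San Francisco". In the counseling arm, Section 4.4.3 has the community health worker explore barriers to recommending vaccination; "Then they will advise how to initiate conversations about RSV vaccination". The worker also gives the participant a written action plan.

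The primary outcome (Table 1) is the self-reported average proportion of contacts aged 50 or older with whom the participant discussed RSV vaccination by 60 days. On the network survey, Section 2.1 states that "Names will not be collected in the social-network survey".

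**The concern.** The two criteria look parallel but do different work. In Motivate the rule protects the trial from within-household contamination. In Activate the same list of aims protects only against carry-over from the earlier aims.

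Activate is the more exposed of the two trials. Its active ingredient is advice on how to raise a topic with relatives, and its outcome is whether that topic was raised. A text-only participant living with a counseled one could pick up the advice, see the action plan, or be drawn into the conversations. The likeliest result is more discussion in the control arm and a diluted contrast.

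The opposite is also possible. If housemates list the same older relatives, one may raise RSV vaccination so that the other does not need to, which would widen the contrast. Either way the estimate would no longer cleanly describe the effect of counseling.

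The problem is awkward to repair after enrollment. Shared relatives cannot be matched by name, and the protocol does not call for a household identifier.

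**Working it through.** **Step 1: can housemates enter opposite arms?**

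| Rule | Motivate (Aim 2) | Activate (Aim 3) |
|---|---|---|
| Aims named in the household exclusion | 1, 2 | 1, 2 |
| Covers its own trial? | Yes | No |
| Unit of randomization | Individual | Individual |
| Stratification | Sex only | Sex only |

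No other section restricts Activate to one person per household, allocates by household, or mentions household clustering. Two co-residents are therefore eligible. Two people of the same sex who fall in the same block of 2 are certain to be in opposite arms. Otherwise the chance is about one half.

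**Step 2: the plan's own power figure.** Section 9.3.1 gives an SD of 0.3, α = 0.05 (taken as two-sided), a 10-point difference, and states "with 175 participants/arm we will have 80% power".

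- Required n per arm = 2 × 0.3² × (1.960 + 0.842)² / 0.10² = 141.3, so 142.
- Two-sample t power at 175 per arm is 87.5%.
- With the 10% attrition that the section assumes for binary outcomes, n = 175 × 0.9 = 157.5 per arm and power is 83.9%.

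The stated 80% is thus conservative, and there is some slack.

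**Step 3: illustrative dilution.** The protocol gives neither a co-enrollment nor a spillover rate, so these are assumptions: half of co-resident pairs are split between arms, and the control member of a split pair gains half of the counseling effect.

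Effect = 10 × (1 − share co-enrolled × 0.5 × 0.5)

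| Share co-enrolled | Effect (points) | Power, 157.5 per arm | Power, 175 per arm |
|---|---|---|---|
| 0% | 10.00 | 83.9% | 87.5% |
| 5% | 10 × (1 − 0.0125) = 9.875 | 82.95% | 86.7% |
| 20% | 10 × (1 − 0.05) = 9.50 | 80.0% | 84.0% |

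Eighty percent power needs 9.50 points at 157.5 per arm (5.0% dilution) and 9.01 points at 175 per arm (9.9% dilution). Under these assumptions the break-even shares are 0.050 / 0.25 = 20% and 0.099 / 0.25 = 39.6%.

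The split fraction matters. If every pair were split, as for same-sex housemates sharing a block, 20% co-enrolled would give 10 × (1 − 0.20 × 1 × 0.5) = 9.0 points. Power would then be about 76% at 157.5 per arm and 80% at 175.

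**Step 4: precision.** For households of two, with correlation ρ and share f co-enrolled, the variance multiplier is 1 + fρ(1 − 2 × split). With half the pairs split it equals 1, so random splitting brings no variance inflation. If household members are deliberately kept in one arm, it is 1 + fρ. With f = 0.20 and an assumed ρ = 0.3 that is 1.06, and power for 10 points becomes 81.7% at 157.5 per arm or 85.5% at 175.

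**The case against.** The strongest reply is that the harm is speculative and small. No section gives a co-enrollment rate, the direction of bias is uncertain, and the design has slack: 142 evaluable per arm suffice against 175 planned. Under the half-split, half-spillover assumptions, about 20% of the sample (70 of 350 enrolled) would have to be co-enrolled before power dropped below 80%, even after attrition. This stands, and it limits the size of the claim. It does not remove the point, because spare power does not correct a biased contrast.

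Section 7.2.2.1 says that Activate's enrollment, randomization and delivery procedures are identical to those of Aim 2, which might be read as importing the Motivate rule. But it speaks of procedures, while eligibility is set in Table 4, where the two rows differ in effect. If the Motivate rule was meant to apply, Table 4 does not say so.

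The Activate criterion may also have been written only to keep out people already exposed to the earlier aims. The protocol gives no rationale, so parity with Motivate cannot be shown to be the intent. That is a reason to ask the sponsor to state the intent.

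Finally, the survey does record each contact's age, gender, race/ethnicity, relationship and residence. With a household identifier, shared relatives could be matched approximately. This is fair: the absence of names makes later repair harder but not impossible.

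**Conclusion.** The gap is real. As written, Table 4 lets two co-residents enter Activate, and individual randomization can place them in opposite arms. The Motivate criterion already prevents this for its own trial.

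The size is unknown and probably modest. On the illustrative assumptions, 5% co-enrollment costs about one percentage point of power. At 20% the effect shrinks to 9.5 points, and power after attrition falls to the planned 80%. These figures rest on assumed split and spillover rates and are not forecasts. The most plausible direction is dilution, but widening cannot be ruled out.

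The point deserves action because it touches the primary outcome and is cheap to prevent. It does not threaten the trial's viability. Confidence is medium: the reading of the text is firm, while the practical impact is not known.

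**What to change.** In Table 4, add Aim 3 to the aims listed in the Activate household exclusion, so that it covers Aims 1, 2 and 3. This is a small change to an existing screening question and works best if made before Activate enrolls. It costs a slightly smaller recruitment pool. Relatives living apart remain eligible, so spillover is reduced rather than removed.

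If co-enrollment in Activate is intended, the protocol should say so, record household at enrollment, assign members of a household to the same arm, and use an analysis that accounts for household clustering. That costs some precision: with 20% co-enrolled and an assumed correlation of 0.3, variance rises by 6% and power after attrition falls from about 84% to 82%.

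A minor related matter for the sponsor to reconcile is whether the Motivate row should also name Aim 3, since an older co-resident of an Activate participant can at present still enter Motivate.

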## 5.2. Recruitment Methods for Aims 1-3

### 5.2.1. Recruitment

Bilingual study staff in partnership with community health workers will recruit eligible participants among people who are receiving services or attending community cultural or health fairs at Latino Task Force (LTF) community sites, CBOs affiliated with the Latino Task Force, or other events in the community. Study team will present the study to Latino Task Force community

meetings. Staff and community health workers will distribute IRB-approved flyers about the study at community-events and answer questions about the study. While CHWs will participate in outreach, enrollment will be done by UCSF study staff. Information about the study will be shared at Latino Task Force meetings and affiliated CBOs will receive recruitment flyers, that they can also post and share with client. If a client expresses interest in the study, the study staff will follow-up with the client to discuss the study further, screen for eligibility, and set a date for the baseline visit if the individual is interested in participating.

### **5.2.2. Participant Incentives**

Participants will receive a gift card or cash incentive as compensation for their time. The amount of the incentive is suitable to compensate for time and transport, without being coercive and the amount has been reviewed with community partners. Incentive amount will be based on time and participants can receive up to the following amounts in gift card or cash:

- (1) Aim 1 vaccine confidence survey: up to \$20
- (2) Aim 1 Community Advisory Board Meetings up to \$60 per 60-90 minute sessions
- (3) Aims 1-3 90 min in-depth interviews over one study visit: up to \$100
- (4) Baseline and Endpoint 30-minute Questionnaires for Aim 2 and Aim 3: up to \$40 at Baseline visits and up to \$40 for Endpoint visits
- (5) Participation in CHW Counseling Session 30 minutes: Up to \$30

### **5.3. Inclusion of Women and Minorities**

All participants in this study will self-identify as Latino and will be residents of work in San Francisco. The study is focused on Latinos, a health disparity population in the United States, because of the need to increase respiratory virus vaccine uptake in the Latino community. Latinos in the United States are disproportionately impacted by acute respiratory viral infections, and they historically have respiratory virus vaccine uptake compared to non-Latino White people. Women are expected to comprise approximately half of the participants this proposal.

#### **5.3.1. Recruitment of Women and Minorities**

To achieve representation of Latinos and women, we have partnered with the Latino Task Force and community groups that are trusted by the Latino community. in partnership with bilingual bicultural study staff, will recruit eligible participants among people who are receiving services or attending community cultural or health fairs at Latino Task Force (LTF) sites or Community Based Organizations (CBOs) affiliated with the Latino Task Force. The Latino Task Force hosts core activities at the Mission Language Vocational School.

### **5.4. Inclusion Across the Lifespan**

This study will include adult participants aged 18-49 years old (Aim 1b & 3) and  $\geq 50$  years and older (Aims 1a & Aim 2). There is no upper age limit to this study. Children (age  $< 18$  years) are not included in this study as the study outcomes are not appropriate for children, as children are not eligible for RSV vaccination and not able to either discuss RSV vaccination with older adults

or not able to fully understand information being discussed during the Community Health Worker 'activation' counseling session.

## 5.5. Participant Registration

For Aims 2 & 3 (Activate and Motivate trials) a written, signed, informed consent form (ICF) and, for Aim 2 only, a Health Insurance Portability and Accountability Act (HIPAA) authorization must be obtained before any study-specific assessments are initiated. A copy of the signed ICF will be given to the participant. The original will be kept on file with the study records.

For Aim 1 community-based vaccination survey participants will review an informed consent information sheet prior to completing the anonymous survey.

## 6. Study Intervention and Randomizations

### 6.1. Randomization (Aim 2 & 3)

Both Aims 2 and 3 are 2 arm trials and intervention groups are described in 4.3.3 (Aim 2) and 4.4.3 (Aim 2). After enrollment participants will then be randomized to one of two study groups. Randomization will be computer generated, block randomization with random block sizes of 2, stratified by sex.

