**Figure 4: Schema of Aim 2 'Motivate Trial'**

#### 4.3.3. Study Design and Description of Intervention Groups

This is a two-arm randomized type-1 effectiveness-implementation individually randomized trial (Figure 4), with study groups:

**i) Arm 1- Text message nudge from CBO:** Participants will receive an educational flyer from a CHW about RSV vaccination and how to schedule it. Then 4 weeks after enrollment they will receive a text-message nudge, with message content based on findings in Aim 1a. This text message will also provide a flyer with vaccine information and eligibility. A phone number to the CHW team, the LTF hotline, for help with navigation will be provided on the flyer and in the text-message.

**ii) Arm 2: CHW counseling and text message nudge from a CBO:** At enrollment, participants will receive an educational flyer from a CHW, as in Arm 1, and will set up a time for the CHW counseling session. They can select remote (phone or web-based platform such as Zoom) or in-person counseling within 2 weeks of enrollment, and weekend hours will be offered. CHW counseling will consist of a 20-minute semi-scripted conversation grounded in the motivational interviewing principals of Five A's and adapted in Aim 1a. CHWs will assess participants beliefs and knowledge about RSV susceptibility and vaccine effectiveness, safety, and eligibility. They will advise and provide general information on vaccine eligibility and RSV susceptibility. Then, assist by assessing personal or structural barriers to vaccination and providing problem-solving techniques. Then arrange next steps: for navigation to a vaccine provider or interest in a follow-up call. CHWs will write down an action plan and give it to the participant, e.g. call clinic to make vaccine appointment in 5 days or follow-up call with CHW in 1 week. CHWs can provide general education about the vaccines: safety, eligibility, testimonials, but they will refer

individual medical questions to the participant's physician. CHWs will also provide a hotline for any questions or assistance with navigating health and vaccine linkage for participants.

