## 7.2. Randomization and Interventions for Trials

### 7.2.1. Randomization and Interventions for 'Motivate' Trial (Aim 2)

This is a two-arm randomized type-1 effectiveness-implementation individually randomized trial. We will randomize individuals to one of the two study groups (see 8.2.2) with random block sizes of 2 and stratified by sex.

The two randomization groups are described in 4.3.3 and are:

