**Study Group 1: Text message nudge**

**Study Group 2: CHW 'activation' counseling with text-message nudge**

### 7.2.2.1. Study Procedures Aim 3

**Enrollment and Randomization:** Enrollment, randomization, and intervention delivery procedures are identical to Aim 2. We will use block randomization with block sizes of 2, with stratification by sex.

**Baseline Survey:** The 25-minute questionnaire will include (1) RSV vaccine hesitancy questionnaire and demographics used in Aim 1 & 2, (2) questions on capability and confidence in recommending the vaccine, (3) Ego-centric (ego=participant) 1st degree social networks of people  $\geq 50$  years (Figure 7). Using 'name generation' techniques used widely in our prior studies, participants will be asked to list the age, gender, race/ethnicity, type of relationship, residence (district, city) and perceived RSV vaccine status of family and friends age of 50 and above. This number will be used as the denominator for the primary outcome and outcomes for each social network contact named will be assessed during the endpoint survey.

**Endpoint Survey:** Participants will complete a 60-day follow-up survey (in person preferred, but phone possible) to assess the proportion of people in their 'named' network at baseline with whom they discussed RSV vaccination. Participants will be shown the characteristics of each person (relationship, age) 'named' in their 1st degree older adult network and they will answer whether they discussed vaccination with that person, why or why not, and

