**Table 5: Participant Schedule of Activities**

Assessments/Procedures	Screening	Study Intervention Period				End of Study Intervention
		Visit 1 / D1 (+14)	Day 14 (Up to 14 § days after D1)	Day 28	Visit 2 / D 60 (+ 14) ^	
Study Visit / Day (Window, # Days)	Visit 0* (-60 to 0 days to D1)					
Informed Consent 1^	X					
Inclusion/Exclusion Criteria ^	X					
Randomization ^		X				
Baseline Questionnaire ^	X					
CHW counseling session and navigation ^ (Arm 2 only)			X			
Text-message				X		
Endpoint questionnaire ^					X	
Outcome Ascertainment - via medical record or California Immunization Registry						X
In-depth interviews ^†						X

 Informed consent must be obtained prior to any study-specific procedures and may be obtained prior to the screening window.

§Can take place up to 60 days after D1 if needed

^Can be done in-person or remotely (telephone or web-based platform such as Zoom)

\*Can be combined with Visit 1

†For a subset of participants only

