## 9.2. Aim 2 (Motivate Trial) Statistical Considerations

**Study Design:** Two-arm randomized type-1 effectiveness-implementation individually randomized trial.

**Analysis Plan.** We will compare the primary outcome of RSV vaccine uptake within 60 days between the two study arms using two broad statistical approaches: unadjusted analyses to explore average treatment effects and model adjusted estimates to reduce variance and examine effects for subpopulations. First, we will examine the intention-to-treat (ITT) effect, over all participants, for the primary outcome of vaccine uptake using the Fisher exact test. To account for participants which the CHW may not be able to reach, we will examine the average treatment effect on the treated (ATT). Second, we will use targeted maximum likelihood estimation (TMLE), a pre-specified approach to data-adaptively adjust for stratified randomization factors and additional baseline predictors of the outcome in order to improve precision. RSV vaccine uptake will be ascertained through the California Immunization Registry, the medical record, or proof of vaccination from a pharmacy. Using an analogous approach, we will also compare intervention effectiveness on pre-specified secondary outcomes and within pre-specified subgroups: baseline high vaccine hesitancy, low trust of healthcare system, low acculturation (score<3.0), sex. These will be augmented by predictor analyses to elucidate risk factors for poor vaccine uptake, overall and by arm and exploratory machine learning analysis for treatment effect heterogeneity. Additionally, we will examine pathways of intervention action (i.e. direct and indirect effects) using formal mediation analyses, considering mediation by post-baseline trust and perceived benefits in the vaccine. Both predictor and mediation analyses will use TMLE.

**Implementation Outcomes:** We will calculate implementation outcomes using the RE-AIM framework for each, through quantitative and qualitative analyses.

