### **9.3.2. Randomization and Blinding**

Randomization for Aim 2 and 3 are referenced in section 6.1. The study statistician will be blinded to treatment arm.

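### Both trials give 2 as their only block size and print it in the protocol, so staff who know the earlier assignments could foresee up to half of the assignments

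*Protocol*

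**What the plan says.** The block size is stated three times in the Protocol.

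- Section 6.1, for both trials: "block randomization with random block sizes of 2, stratified by sex".
- Section 7.2.1, for Motivate: "with random block sizes of 2 and stratified by sex". This section also points to a Section 8.2.2, which does not exist, so no further detail is found there.
- Section 7.2.2.1, for Activate: "We will use block randomization with block sizes of 2, with stratification by sex". The same paragraph says that the procedures are identical to those of Aim 2.

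Sex is the only stratification factor. On blinding, Section 9.3.2 says only this: "The study statistician will be blinded to treatment arm".

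Four other places bear on the point.

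- Section 4.3.3: at enrollment, Arm 2 participants "will set up a time for the CHW counseling session"; Arm 1 has no such step. In Activate, too, only Arm 2 has counseling (Section 4.4.3).
- Section 5.2.1: study staff do the enrolling, and they "screen for eligibility, and set a date for the baseline visit" for people who express interest.
- Table 5: the screening window opens up to 60 days before D1 (minus "60 to 0 days to D1"). Consent and the baseline questionnaire come before randomization.
- Section 9.2: the ITT effect in Motivate is examined first, "for the primary outcome of vaccine uptake using the Fisher exact test".

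**The concern.** The word random needs at least two sizes to choose from, and the Protocol names one. Read literally, every block has length 2, and anyone with the Protocol knows it. In a two-arm trial with equal arms such a block is either Arm 1 then Arm 2, or the reverse. Once the first member of a same-sex pair is assigned, the second is settled.

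Each trial has only two sequences to follow, one per sex. The arm becomes visible when counseling is booked, and nobody except the statistician is said to be blinded. A staff member who knows the earlier assignments, and whether a pair is open, could know the next arm before deciding whom to screen or when to bring a candidate in. In Motivate, people already inclined toward vaccination could be entered when counseling is next, even without intent. In Activate, the parallel risk is people inclined to talk with relatives.

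The unadjusted Fisher test would carry such selection in full. The planned TMLE adjustment could remove the part explained by measured baseline variables, but not the rest.

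**Working it through.** **Inputs from the Protocol.** Block size 2, two arms, strata by sex (Sections 6.1, 7.2.1, 7.2.2.1); 200 per arm and 28% text-arm uptake in Motivate (Section 9.2.1); 175 per arm and SD 0.3 in Activate (Section 9.3.1); detectable ITT effects of 10 points in both. The Protocol states no predictability figure, so there is none to reproduce.

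**Step 1: predictability.** All balanced blocks of each size were enumerated. An assignment is determined when one arm is used up within the block. The guesser picks the arm that is behind and tosses a coin when the arms are level.

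| Block sizes | Determined | Correct guesses |
|---|---|---|
| 2 | 50% | 75% |
| 4 | 33.3% | 70.8% |
| 6 | 25% | 68.3% |
| 8 | 20% | 66.6% |
| 4/6/8 at random, sizes unknown to the guesser | not applicable | about 68% |
| 4/6/8 at random, sizes known but boundaries unknown | 2.3% | about 72% |

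For blocks of 2, the correct-guess rate is 0.5 × 100% + 0.5 × 50% = 75%, against 50% under simple randomization. The counts are 400 / 2 = 200 in Motivate and 350 / 2 = 175 in Activate (174 if both sex strata are odd in size).

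**Step 2: bias.** Let s be the share of predictable slots that staff recognise and act on. Let D be the outcome difference between people entered at known Arm 2 slots and people entered at known Arm 1 slots. Neither is in the Protocol; both are assumptions. Half of each arm's slots are predictable, so

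bias = 0.5 × s × D.

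- D = 10 points: 0.5 × 0.25 × 10 = 1.25; 0.5 × 0.50 × 10 = 2.5; 0.5 × 1 × 10 = 5. Simulation gave the same values.
- Range for D of 5 to 15 points and s of 25% to 100%: from 0.5 × 0.25 × 5 = 0.6 to 0.5 × 1 × 15 = 7.5 points.

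**Step 3: the same model under varying sizes.** With correct-guess rate g the bias is (2g − 1) × s × D, which gives 0.5 × s × D at g = 0.75. For D = 10 and s = 1:

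- sizes 4/6/8, unknown to the guesser: (2 × 0.68 − 1) × 10 = 3.6 points;
- set of sizes known: (2 × 0.718 − 1) × 10 = about 4.4 points.

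**Step 4: false-positive rate with no true effect.** For Motivate, the Fisher test was enumerated exactly with 200 per arm and overall uptake of 28%. For Activate, a two-sided z test was assumed, with standard error 0.3 × √(2/175) = 0.0321. At a bias of 5 points, 0.05 / 0.0321 = 1.56, and P(Z > 1.96 − 1.56) is about 34%.

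| Bias (points) | Motivate | Activate |
|---|---|---|
| 0 | 3.9% | 5.0% |
| 1.25 | 4.7% | 6.8% |
| 2.5 | 7.0% | 12.2% |
| 5 (upper bound for D = 10) | 17.1% | 34.4% |

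With 157 per arm in Activate after 10% attrition, the last value is 31.5%.

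**The case against.** The strongest points on the other side are these.

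- **The authors may have meant varying sizes, perhaps multiples of 2.** Both passages that cover Motivate say random. This is possible, but no other size is printed, and the Activate section gives a plain 2 while declaring its procedures identical to Aim 2. Even on the kinder reading the text needs correcting, because whoever builds the list will follow what is written.
- **Foresight is inferred, not stated.** The Protocol does not say that the person screening the next candidate sees earlier assignments, and custody of the list may be set out elsewhere. This stands as a limit: 50% is a ceiling that depends on that knowledge. Recruitment at several venues also makes it harder to exploit, and the first member of each pair stays unpredictable.
- **A long gap before D1 works against prediction.** Other people of the same sex may be randomized meanwhile, and the screening visit may be combined with Visit 1. This is partly right. The window blurs which slot a candidate will take, but it also leaves latitude over when D1 falls. The risk is greatest close to randomization.
- **Randomization already follows consent and baseline.** That order protects the baseline answers. It does not stop foresight when someone decides whom to book.
- **The remedy does not remove guessing.** This is correct. In the model, the worst case for a 10-point difference falls from 5 points to about 3.6, or about 4.4 if the sizes are known, a reduction of roughly 12% to 28%. The larger gain is in certainty: from half of all assignments to about 2%.
- **The upper-end error rates assume that every predictable slot is exploited, and the Activate test is an assumption.** Both are true, and the figures should be read that way.

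**Conclusion.** The concern holds. The three passages cannot be read consistently as random block sizes, and the only rule that can be carried out as written is a disclosed, fixed block of 2. It determines up to 200 of 400 assignments in Motivate and up to 175 of 350 in Activate for staff who know the earlier ones in the stratum.

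The predictability figures follow from the design alone. The bias does not: it rests on an assumed outcome difference and an assumed share of slots acted on. Nothing in the Protocol shows that staff would act on foresight. At a 10-point difference the bias reaches half of the effect the trials are sized to detect only if every predictable slot is used; at a 25% share it is 1.25 points and barely moves the false-positive rate in Motivate. The change should be made because the weakness affects both trials and costs little to remove.

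**What to change.** In Sections 6.1, 7.2.1 and 7.2.2.1, replace the block-size wording with one common statement, for example: randomly permuted blocks of randomly varying size, stratified by sex; block sizes held in a restricted randomization document and withheld from recruiting, enrolling and CHW staff; each assignment released only after consent and the baseline survey are complete. Keep the actual sizes (4, 6 and 8, for example) in the restricted document and out of the Protocol. The release clause only makes the order in Table 5 explicit; the protection comes from the varying, withheld sizes.

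The cost is a new computer-generated list, one restricted document and three wording changes. No sample size, endpoint or visit changes. With a largest block of 8, the arms can differ by at most 4 participants within a sex stratum (simulated 95th percentile: 2 in a stratum of 200). The strata would hold about 200 in Motivate and 175 in Activate if women are about half, as Section 5.3 expects, so the balance by sex sought in Section 9.3.3 is kept.
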